3. STUDY DESIGN

3.1 DESCRIPTION OF THE STUDY

Ocrevus[™] is the first FDA approved disease-modifying treatment for primary progressive MS as well as relapsing MS [3]. In the clinical trials considered by the FDA (OPERA I/II, ORATORIO), the highest Expanded Disability Status Scale (EDSS) included in the participants was 5.5 (OPERA I/II) and 6.5 (ORATORIO) [4]. The EDSS score is heavily weighted on walking ability and is not a useful measurement for UE function [5,6]. The primary endpoint in the primary progressive MS trial with Ocrevus[™] was EDSS and in the relapsing MS studies, EDSS was used as a secondary endpoint. The Multiple Sclerosis Functional Composite (MSFC) score (Z score), a composite of quantitative measure of walking speed, upper limb coordinated movement (9 Hole Peg Test/9HPT) and cognitive function, was obtained as a secondary clinical

measure with scores being favorably higher in patients treated with Ocrevus[™] (OPERA I/II). The z score, however, is not very useful in delineating which of the three clinical functions was maintained or showed less progression given that three domains are included in the score [7,8,9]. Data presented recently from the Oratorio trial analyzed the intention to treat population of PPMS patients and the subgroups of patients with upper extremity functional impairment using the 9HPT; results demonstrated reduction in risk of clinical progression in upper extremity disability in patients treated with Ocrevus compared to placebo. There was improvement in the change from baseline to week 120 in 9HPT time in treated patients. Abnormal baseline 9HPT was defined as >25 seconds and upper extremities were defined as "better hand" and "worse hand", each individually tested, with clinical progression determined at 12 and 24 weeks in 3 sub-categories of progression: lengthened time of 9HPT >15%, >20% and 25%. [10]

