3.2 RATIONALE FOR STUDY DESIGN

We anticipate the use of Ocrevus[™] in patients with progressive disease which includes those with advanced disability, regardless of a dearth of data to guide the prescriber regarding its effect in this population. The rational for this study is to gain information which will help the prescribers of Ocrevus[™] answer the question "Will Ocrevus[™] help me if I have hand or arm weakness?" especially if posed by a more advanced MS patient (EDSS 4.0-8.0 with UE involvement) than those included in the clinical trials. In previous trials (ORATORIO), the included patients were only those diagnosed with primary progressive MS and their entry EDSS was of a lower disability range (3.0-6.5) than those proposed in this study. Therefore, the results cannot be completely extrapolated to the population of multiple sclerosis patients with more advanced disability that we propose to study. We aim to identify MS patients that have weakness in at least one upper limb, knowing that delaying disability affecting the functional use of the UE will help patients remain independent for some activities of daily life and will contribute to an improved quality of life.

The importance of choosing validated upper limb outcome assessment tools cannot be emphasized enough. The Nine-Hole Peg Test (9HPT), an objective measure of manual dexterity, which is incorporated into the MSFC, is a widely used measure across most clinical trials in multiple sclerosis populations.

The EDSS is an ordinal scale of neurological disability designed specifically for MS patients and will provide specific quantitative measure of upper limb strength, sensory impairment and ataxia of the upper limb with each Functional System Subscore. This score will aid in deciphering limitations due to tremors or ataxias.

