The Test d'Evaluation de la performance des Membres Supérieurs des Personnes Agées (TEMPA) has been previously studied for validity in clinical trials and specifically in multiple sclerosis patient populations and there was a strong correlation between the TEMPA and 9HPT. [11, 12] The TEMPA consists of 9 tasks that mimic tasks of daily living such as picking up a jar, pouring water from a pitcher, handling coins, writing on an envelope and opening a pill container, as examples. The tasks are assessed by a rater by measuring speed of execution (seconds) and by functional rating of the subject's independence in performing them using an ordinal scale of 0 (completed without difficulty) to -3 (could not complete the task). The test provides a unilateral and bilateral score and evaluates different grasp, grip and pinch functions. Obtaining baseline scores and sequential measurements will allow us to graph scores over time for each patient and assess the change. This type of testing would give us a clear picture of any changes in UE functionality and would highlight meaningful clinical data that would be easily translated to patients- stability of function vs clinical progression >20% change from baseline. This key data would be a helpful reference when discussing starting treatment with Ocrevus™ in this population of patients.

The normative values available for the TEMPA were obtained in the elderly (ages 60-80, men and women). The speed of execution of the 9 tasks in each hand takes about 70 to 80 seconds to complete in this population. [12] When one reviews the validity study of the TEMPA in MS patients [average EDSS was 7 and age median was 46 years old], this same parameter took them between 100 and 400 seconds [1 and 1/2 to 6 minutes] to complete.

Schwid et al in 2002 showed that MS patients did not vary from their baselines in performing the 9HPT by >20% day-to day and therefore the if there was change measured >20% from their baseline this was stipulated to indicate change in function [13].

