4.0 MATERIALS AND METHODS

This is a 24-month, prospective, observational study which will be conducted at the University of South Florida (USF) MS Center. On average 80-100 patients a week are seen at the study site. This large patient population offers a suitable number of potential candidates in order to meet the enrollment goal. This study will be conducted in adult multiple sclerosis patients who have upper extremity impairment and must satisfy the approved therapeutic indication for Ocrevus[™]. Decision to treat with Ocrevus[™] must precede enrollment. We anticipate enrollment will be random and open to any patient that meets the criteria below which will aid in the evaluation of our results to the general MS population. The targeted population are those patients that more often rely on their upper extremity function for activities of daily living due to impairment in other systems such as gait.)

Every effort to maintain consistency (by use of the same rater) for the administration of the upper extremity assessments will be made. The same instructions for the patient questionnaires will be given at each time point.

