4.2 METHOD OF TREATMENT ASSIGNMENT

There is no randomization in this study. Stratification of results by age and baseline UE strength may occur in the analysis.

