4.5 STUDY ASSESSMENTS

4.5.1 Overview of Study Visits

Screening/Baseline Visit (Day 0)

After the ICF is signed, the following information/assessments will be conducted:

- Review of medical history
- Review of inclusion/exclusion criteria
- Documentation on concomitant medications
- Demographic information
- Vital signs
- Measurement of UE function (TEMPA, 9HPT)
- Questionnaires (UEFI, FSS, SDMT, MUSIQOL)
- Physical examination/EDSS

Quarterly Visits* (Months 3, 9, 15, 21)

- Changes in concomitant medications and AE
- Questionnaires (UEFI, FSS, SDMT, MUSIQOL)
- Vital signs
- Interval history

*In the case of financial or physical limitations with the patient, the quarterly visits will be conducted via phone. In these instances, vital signs will not be obtained, as this will not affect the standard of care.

Semi-annual visits (before Ocrevus[™] infusion) (Months 6, 12, 18)

- Changes in concomitant medications and AEs
- Review of concomitant medication and AEs
- Questionnaires (UEFI, FSS, SDMT, MUSIQOL)
- Physical examination/EDSS
- Vital signs
- Interval history
- Measurement of UE function (TEMPA, 9HPT)

Month 24 End of study (EOS)/Early discontinuation visit

In the event Ocrevus[™] is discontinued prior to the end of the 24-month study, the patient will be asked to come in for EOS procedures. Any AEs attributed to Ocrevus[™] in the opinion of the investigator, will be followed until resolved, and documented in the patient study chart.

- Review of concomitant medication and AEs
- Patient questionnaires (UEFI, FSS, SDMT, MUSIQOL)
- Physical examination/EDSS
- Vital signs
- Interval history
- Measurement of UE function (TEMPA, 9HPT)

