4.9.3 Efficacy Analysis

a. Primary Endpoint

1. TEMPA scores after 24 months of Ocrevus[™] treatment. Paired sample t-test to compare the 24 month measurements to the baseline measurements.

Mean within-patient changes from baseline through 24 months (TEMPA). Oneway repeated measures ANCOVA for TEMPA scores from baseline, 6 months, 12 months, 18 months, 24 months which will account for baseline characteristics (baseline disability level). A soft stratification will be applied so that recruitment will aim to include a spread of types of patients, those below overall EDSS of 6.0 and those above 6.0. If more than 2/3 of total enrollment is in one of the categories, the study team will reestablish efforts to recruit for the other cohort.

If data does not have normal distribution, then other non-parametric analysis will be employed (such as sign test for TEMPA functional score).

The threshold to determine a significant clinical change will be >20% from baseline value. This clinically significant difference is estimated based on data from the Oratorio trials that showed progression among both groups (placebo and OcrevusTM) but to a lesser extent in the OcrevusTM arm with an established clinically significant threshold of 20% (data will be requested from sponsor for use to review 9HPT results for the abnormal function at baseline group of patients). Measures will be collected and analyzed as units of time (seconds) and as functional scores on an ordinal scale that range from 0 to -3 (0 indicating

no signs of dysfunction).Ad hoc analysis may occur that includes evaluation of patients with significant clinical changes versus those that did not have significant clinical change based on any of the subscales within the TEMPA or physical exam. We will review >15%, >20% and >25% [in better hand and in worse hand] change from baseline with increases in time implying clinical progression and stability or decrease in time implying stability or improvement in function

b. Secondary Endpoints

Pearson correlation coefficients will be calculated to evaluate correlations between UE function (measured by TEMPA and 9HPT) primarily at baseline but also at each time point over the 24-month time period to compare patient responses on the UEFI, FSS, and MUSIQOL. Correlations with the primary endpoint scores and the SDMT will also be analyzed for any indication of new cognitive impairment that may interfere with the interpretation of the results.

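### Does leaving EDSS exactly 6.0 out of the soft recruitment balance rule, and planning no result by baseline EDSS, call for a change to the plan?

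*Combined protocol and SAP*

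**What the plan says.** The recruitment rule is in section 4.9.3 of the combined protocol and SAP, under the primary endpoint. Recruitment aims for a spread of patients, "those below overall EDSS of 6.0 and those above 6.0. If more than 2/3 of total enrollment is in one of the categories", and the consequence is a renewed effort to recruit the other cohort. It is not a cap or an exclusion. Section 4.1.2 admits EDSS 4.0 to 8.0, so 6.0 is eligible. Section 4.9.6 plans data on 30 patients, with up to 35 screened to cover screen failures and early withdrawals, and states that the sample size was not calculated.

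On the use of EDSS in reporting:

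- Section 3.1 gives the earlier trials' ceilings: the highest EDSS "included in the participants was 5.5 (OPERA I/II) and 6.5 (ORATORIO"). The same section says EDSS depends heavily on walking and is of little use as a measure of upper-extremity function.
- Section 3.2 motivates the study by the question of benefit, "especially if posed by a more advanced MS patient (EDSS 4.0-8.0 with UE involvement) than those included in the clinical trials", and plans to "graph scores over time for each patient".
- Section 4.0 targets patients who rely on their arms "due to impairment in other systems such as gait".
- Section 4.2 says: "Stratification of results by age and baseline UE strength may occur in the analysis". EDSS is not listed.
- Section 4.9.3 plans a repeated measures ANCOVA "which will account for baseline characteristics (baseline disability level").
- Section 4.9.2 promises descriptive baseline characteristics. Section 4.5.1 lists "Physical examination/EDSS" at the baseline visit, so the score is collected.

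**The concern.** There are two points.

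First, the two recruitment groups do not cover the eligible range. A patient at 6.0 adds to the denominator of the two-thirds check but to neither numerator. Such patients can only make the trigger harder to reach, so the omission weakens a safeguard that the investigators chose. Two staff members who quietly placed 6.0 on different sides could also disagree about whether recruitment is unbalanced.

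Second, the study is justified largely by patients more disabled than those in the earlier trials, yet the percentage remaining stable is planned as one pooled figure. The balance rule can be met with few patients, or none, above EDSS 6.5. A reader could then be left unsure whether stability was seen in the patients who motivated the study. At stake is how far the result generalises, not whether the primary comparison is valid.

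**Working it through.** The documents give no figure on this point to reproduce, so the check applies the rule directly.

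**Inputs.** Planned enrolment N = 30 and a screening limit of 35 (section 4.9.6). Trigger: more than 2/3 of total enrolment in one group (section 4.9.3). Eligible EDSS 4.0 to 8.0 (section 4.1.2). The documents give no EDSS distribution, so the share at exactly 6.0 and the split of the remainder are assumptions.

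**Threshold.** The trigger fires when 3k > 2N for either group count k. With N = 30 this means k > 20, so k must be at least 21.

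**Splits at N = 30**

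| Below / at 6.0 / above | Lower group as written | Lower group if 6.0 counts as low | Trigger changes? |
|---|---|---|---|
| 20 / 1 / 9 | 20/30 = 66.7% | 21/30 = 70.0% | yes |
| 16 / 6 / 8 | 16/30 = 53.3% | 22/30 = 73.3% | yes |
| 10 / 6 / 14 | 10/30 = 33.3% | 16/30 = 53.3% | no |

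In the last row the upper group is 14/30 = 46.7% as written and 20/30 = 66.7% if 6.0 counts as high, which also does not fire. In every row the wording gives a single answer: patients at 6.0 enter the denominator only.

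**How often it matters.** Let the counts (a, m, b) below, at and above 6.0 be multinomial with N = 30, and sum 30!/(a! m! b!) × p_a^a × p_m^m × p_b^b over the splits where the trigger differs from the rule as written.

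| Assumed share at 6.0 | Rest 60:40 below:above, 6.0 as low | Rest 60:40, 6.0 as high | Rest 50:50, either side |
|---|---|---|---|
| 5% | 13.6% | 0.2% | 2.9% |
| 10% | 26.0% | 0.7% | 6.4% |
| 20% | 48.2% | 3.5% | 17.5% |

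The largest cell needs a 20% share at 6.0, a 60:40 split, and 6.0 placed on the larger side. All cells refer to full enrolment. At that point at most 35 − 30 = 5 more patients may be screened, and those places are held for screen failures and withdrawals. Renewed recruitment can therefore shift the mix very little.

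**What a result by EDSS could show.** The rule allows 20 below 6.0 and 10 at 6.5 (20/30, no trigger), which leaves nobody at 7.0 or above and an empty upper row. If patients are present there, suppose for illustration that 24 of 30 are stable (80%). With 6 patients at 7.0 to 8.0, between max(0, 24 − 24) = 0 and 6 of them are stable. With 10, between 24 − 20 = 4 and 10 are. These bounds hold for any subgroup inside any pooled percentage. Exact (Clopper-Pearson) 95% limits, from the Beta quantiles Beta(0.025; x, n − x + 1) and Beta(0.975; x + 1, n − x), are:

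| Stable / n | 95% interval |
|---|---|
| 5 / 6 | 36% to 99.6% |
| 8 / 10 | 44% to 97% |
| 16 / 20 | 56% to 94% |
| 24 / 30 | 61% to 92% |

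The intervals for 8/10 and 16/20, the same observed percentage in two unequal groups, overlap almost completely.

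**The case for a change.** The strongest case for a change is that it would cost almost nothing: one phrase to place 6.0, and one descriptive table from data already collected. A split written down before the 24-month data are seen is also more credible than one chosen afterwards. The omission has a direction, since the rule as written can never fire more often than a version that assigns 6.0. And section 3.2 does frame the rationale by EDSS, so a reader will want to know how the most disabled patients fared.

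Much of this stands. The omission is real, its direction is as described, and a descriptive display by EDSS would be reasonable. Low cost alone does not make a change necessary, however. The protocol has its own reason not to organise an upper-extremity outcome by EDSS, namely that the scale mainly reflects walking, and section 4.2 names age and baseline arm strength as possible strata instead. The most obvious table, 4.0 to 6.5 against 7.0 to 8.0, would also misclassify relapsing patients at 6.0 to 6.5. They already exceed the 5.5 ceiling of the relapsing trials but would sit in the lower row.

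**Conclusion.** No change to the plan follows. Leaving out 6.0 is a wording slip in a soft recruitment aim. The rule is determinate as written, turns nobody away, and does not touch the paired t-test, the ANCOVA or the 20% stability threshold. A study team that meets a patient at 6.0 can place that patient sensibly in its recruitment log. The worst outcome is that a renewed recruitment effort starts a little later or not at all.

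The missing breakdown by EDSS is a fair omission in an uncalculated pilot of 30. Baseline descriptives can show how many advanced patients enrolled, and the per-patient graphs can show how each of them did. Any subgroup percentage would carry an interval too wide to answer the question (44% to 97% for 8 of 10), and the upper row might be empty. The authors may add such a listing, and any statement about disability beyond the earlier trials should match the patients actually enrolled there, but the planned results are sound without it.

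The trigger probabilities (0.2% to 48%) rest on assumed shares at 6.0, assumed splits and full enrolment. The numbers stable are illustrative. The conclusion depends on neither: it rests on the rule being soft and separate from the primary analysis.

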In a pilot study where a technology enhanced training program for improving upper limb muscle strength in MS patients the TEMPA was used at baseline and 8 weeks later, and there was a trend towards statistical significance of improvement in function with TEMPA change of 20 to 40 seconds [14]. Since the 9HPT and TEMPA have been show to correlate and there are numerical values measured in both, we plan to emulate the Oratorio study and look at >15%, >20% and >25% [in better hand and in worse hand] change from baseline with increases in time implying clinical progression and stability or decrease in time implying stability or improvement in function.

The Jamar dynamometer is validated tool often used by occupational therapist to measure grip strength [15]. Grip strength is an important part of daily living tasks and can give clinicians insight into patient restrictions and clinical changes.

The Upper Extremity Functional Index (UEFI) is a self-report questionnaire that has been found reliable, valid and sensitive as a patient- reported outcome measure tool for quantifying UE function rated on a 5-point Likert scale This 20item measure is recommended in research and clinical setting due to its unidimensionality: it measures only UE function [16,17]. Scores range from 0 to 60 with lower scores indicating more functional difficulty. It has been used in several studies in patients with musculoskeletal upper extremity problems, to include patients with MS, and UEFI scores correlated with mean 9-HPT scores. [18] We anticipate that patients in our study will have perceived stabilization of their upper extremity function and plan to use the UEFI to measure this by means of its validated 9 points of change from baseline for minimal detectable change in function.

The Symbol Digit Modalities Test (SDMT) is a validated measure used to assess mental processing speed in MS clinical trials and has an oral response version. There is evidence that cognitive measures may correlate with upper extremity function. This can possibly be explained by a cerebral relationship between motor function and cognition [19]. As a secondary measure we will collect SDMTs at each visit to explore correlations with upper extremity function, as well as QoL measures.

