3.3.1 Primary Outcome Measure

No significant change in UE function over 24 months after initiation of Ocrevus™ measured objectively by measure of time to completion (seconds) and functional

scores on TEMPA (0 to -3). The hypothesis is that there is (stabilization) no significant change (within 20%) of TEMPA score from baseline to 24 months

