4.9.5 Missing Data

Study staff will work to ensure missing data is minimized. If there are less than two percent of time points missing, then during analysis, last value carry forward imputation will be used. If greater than two percent missing, multiple point imputation measures will be used.

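### The 20% stability threshold comes from timed 9HPT data but is not limited to TEMPA time; on the ordinal functional score it is undefined at a baseline of 0 and arbitrary elsewhere

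*Combined protocol and SAP*

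**What the plan says.** Section 3.3.1 makes both TEMPA time in seconds and the TEMPA functional score the primary outcome, and then states one hypothesis: "The hypothesis is that there is (stabilization) no significant change (within 20%) of TEMPA score from baseline to 24 months". Section 2.1 defines stabilization as a change of at most 20% in upper extremity function. Section 4.9.6 says the study will evaluate the percentage of patients who stay within 20% of baseline.

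Section 4.9.3 gives the general rule, "The threshold to determine a significant clinical change will be >20% from baseline value", and shortly afterwards says that measures will be "analyzed as units of time (seconds) and as functional scores on an ordinal scale that range from 0 to -3". If the data are not normal, "other non-parametric analysis will be employed (such as sign test for TEMPA functional score").

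The basis for 20% is timed throughout. Section 3.1 cites progression in ORATORIO as "lengthened time of 9HPT >15%, >20% and 25"%. Section 3.2 cites the finding that "MS patients did not vary from their baselines in performing the 9HPT by >20% day-to day". Section 4.9.3 refers again to ORATORIO and 9HPT data. Section 3.2 carries the cut-offs to the TEMPA with this reasoning: "Since the 9HPT and TEMPA have been show to correlate and there are numerical values measured in both".

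Section 3.3 describes the functional score. Each task is rated 0 (best) to -3 (not completed), a total is formed from unilateral and bilateral tasks, unilateral and bilateral scores are also analysed individually, and scores typically run from 0 to -50.

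**The concern.** A percentage of baseline makes sense for seconds, which have a true zero and equal units. An ordinal score whose best value is 0 has neither property. Correlation between the TEMPA and the 9HPT, and the fact that both yield numbers, may support carrying a cut-off from one timing to another. They do not support carrying it to a rating scale.

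At stake is the stable percentage that section 4.9.6 sets as an aim. If the rule is followed as written for the functional part of the primary outcome, some patients may be impossible to classify. The rest would be classified by a bar that depends on where they started and on which of three scores the analyst picks. With about 30 patients, a few such decisions visibly move the result.

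**Working it through.** The plan has no sample size or power figure to reproduce: section 4.9.6 says that 30 is not a calculated number. The check is direct arithmetic on the rule.

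**Inputs.** Threshold: more than 20% of baseline (4.9.3). Rating per task: 0 to -3 (3.3, 4.9.3). Total: typically 0 to -50 (3.3). Planned patients: 30 (4.9.6). TEMPA visits: baseline and months 6, 12, 18 and 24, so 5 (4.5.1).

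**1. Baseline of 0.** Percent change = 100 × (change in points) / |baseline|. At 0 this divides by zero, even for a patient who falls to -3 on a task. Section 4.1.2 asks for grade 4/5 weakness in at least two muscles of one limb. That does not exclude a score of 0, and from 0 the only possible change is worsening.

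**2. A single rating.** One level = 100 / |baseline|: 100% from -1, 50% from -2, 33.3% from -3. Every one-level change exceeds 20%, so staying within 20% means no change at all.

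**3. The total.** The smallest loss of k points that exceeds 20% satisfies k / |baseline| > 0.20, that is 5k > |baseline|, so k = floor(|baseline| / 5) + 1.

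| Baseline total | Points needed |
|---|---|
| 0 | undefined |
| -1 to -4 | 1 |
| -5 to -9 | 2 |
| -10 to -14 | 3 |
| -15 to -19 | 4 |
| -20 to -24 | 5 |

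The same 2-point loss is 2/8 = 25% from -8 (a change) and 2/12 = 16.7% from -12 (stable).

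**4. Which score.** Section 3.3 names total, unilateral and bilateral scores. Sections 2.1, 3.3.1, 4.9.3 and 4.9.6 do not say which one carries the threshold. Steps 2 and 3 show that the answer depends on it.

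**5. Weight of one patient.** 1/30 = 3.3 percentage points of the stable percentage.

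**6. Time: a patient more than 20% faster.** Sections 2.1, 3.3.1 and 4.9.6 define stable as within 20%, and section 3.3 lists improvement, worsening and stability as separate outcomes. Together these class such a patient as improved. Section 3.2 contrasts stability only with progression, and sections 3.2 and 4.9.3 describe a decrease in time as either stability or improvement. The wording is loose, but the classification can be recovered.

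**7. Time: a task that is not completed.** It is rated -3, but no rule is stated for its time. The consequence depends on what the analyst does.
- If its time is left out of a sum, with other tasks unchanged and equal times per task (assumption), the sum falls by 1/9 = 11.1%. Counting 13 timed performances (4 unilateral × 2 hands + 5 bilateral), it falls by 1/13 = 7.7%. Both read as stable.
- If it is treated as missing, section 4.9.5 says: "If there are less than two percent of time points missing, then during analysis, last value carry forward imputation will be used". Reading time points as patient-visits, there are 30 × 5 = 150. Two percent is 3, so carry-forward applies with 1 or 2 missing.

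**The case against.** The best defence is that 20% was meant for time. The sentence in 3.2 and 4.9.3 that reviews changes above 15%, 20% and 25% by hand speaks only of time, and the sign test is named for the functional score. That reading is plausible, but neither point settles the matter. The hypothesis in 3.3.1 and the threshold sentence in 4.9.3 are not restricted, and both sit beside a statement that both measures are primary or analysed. The sign test is a fallback test of change and does not define who is stable.

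A second objection is that any relative threshold means different absolute amounts: on time, 20% is 20 s from 100 s and 80 s from 400 s. That is true, and varying points alone would not be a fault. The fault is that the documents give no ground for reading ratios on an ordinal score.

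Third, a total of 0 requires every task to be done with ease, in patients with EDSS 4.0 to 8.0 and limb weakness, so it may be uncommon. This stands: the frequency is unknown. The problem in steps 2 to 4 does not depend on it.

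Fourth, the paired t-test and repeated measures ANCOVA need no 20% rule. That also stands, but neither gives the stable percentage.

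A reader might infer more than the documents support:
- **That improvers on time have no category.** Read together, the sections in step 6 class them as improved.
- **That a patient who loses a task will have an old time carried forward and be counted as stable.** Section 4.9.5 speaks of missing time points, and nothing says that inability at an attended visit counts as missing. The loss is also recorded as -3 on the other primary measure. Only the absence of a rule is established.
- **That no scoring level is defined at all.** Section 3.3 defines three; the gap is which one the threshold uses.

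**Conclusion.** The point holds for the functional score. The 20% rule is unrestricted in 2.1, 3.3.1, 4.9.3 and 4.9.6, rests only on timed 9HPT data, and does not work on an ordinal score that is part of the primary outcome. It is undefined at 0, means no change at all on a single rating, and on the total requires between 1 point (at -1 to -4) and 5 points (at -20 to -24) over the range tabulated. This is arithmetic on the plan's own scales and needs no assumption. The number of patients affected cannot be estimated, because the documents give no baseline distribution or SD; each one counts for 3.3 percentage points if 30 are analysed.

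For time the rule is computable. The wording on improvers needs clarifying, and the missing rule for an uncompleted task is a minor gap whose effect is conditional. Neither supports a claim that the time result is invalid.

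**What to change.** 1. In 3.3.1 and 4.9.3, limit the 20% rule to TEMPA time, and have 2.1 and 4.9.6 refer to that definition.
2. Analyse the functional score in absolute points on the total score described in 3.3, with unilateral and bilateral scores as supporting analyses. Report the number and percentage worse, same and better at 24 months with exact 95% confidence intervals, the distribution of point change, and the sign test already named in 4.9.3. Use no percentage threshold.
3. As a clarification for time, report worsened (more than 20% longer), stable (within 20%) and improved (more than 20% shorter). This matches the categories in 3.3. Align the wording in 3.2 and 4.9.3.
4. As a minor addition, state in 4.9.5 that inability to complete a task at an attended visit is not missing data. Report such patients separately on time, with a sensitivity analysis that classes them as worsened.

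The cost is revised wording in the protocol and SAP and slightly more reporting. The objective and hypothesis keep their 20% band for time. The downside is that the functional score no longer has a percentage-based definition of stability, so it is described by direction and size of change instead.
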